2.8. WITHDRAWAL OF SUBJECTS

Subjects who have signed an informed consent form may be withdrawn from this study if they withdraw their consent, or if the investigator determines the subject should no longer continue in the study. Subjects may be excluded early from the study at the discretion of the investigator if continued participation in the trial would in some way jeopardize the subject's health or welfare, or as a result of voluntary withdrawal, being lost to follow-up (LTFU), death, or other reasons not related to SAEs.

Regardless of the reason for withdrawal, data available for the subject at the time of withdrawal, including the reason for withdrawal, will be entered on the Case Report Forms (CRFs). Data collected up to the time of withdrawal may be used by the sponsor and supporting medical device manufacturer for regulatory submissions, publications and other study related data analyses. In cases of withdrawal or LTFU, the study Investigator should document the contact attempts and reasons for subject withdrawal or lost to follow up with other supporting information as requested on the appropriate CRFs.

3. STUDY PROCEDURES

3.1. SCREENING AND INFORMED CONSENT

Patient screening will follow each participating institution's standard of care. A member of the Research Team at the site will review the subject's previously documented standard of care medical information (including CT from the referring doctor) for eligibility and inclusion into the study. Subjects will be approached to obtain informed consent prior to any study-specific procedure. Informed consent will take place in a private environment (e.g. patient exam room), free from distractions. The PI or study

team member will approach the subject at their standard of care clinic appointment or prior to their scheduled bronchoscopy and will explain the study to qualified subjects prior to obtaining consent. All individuals who obtain consent (PI, Sub-investigators, and study coordinators) must have completion certificates for the CITI Human Subjects Research Education Course. Interviews to obtain consent will not follow any stressful situation (e.g. patient being informed he/she may have cancer) and will not be conducted if the patient has received any mind-altering medications or anesthesia. Patients will be assessed for their capacity to consent by the ability to show comprehension of the procedure, ask appropriate questions, and appear properly oriented. A signed copy of all consents and the HIPAA authorization document will also be given to consenting subjects.

3.2. SCREEN FAILURES

Subjects who provide informed consent, but are determined to be ineligible prior to the index procedure (insertion of the cryoprobe into the working channel of the bronchoscope) will be considered screen failures. The reason for screen failure will be documented.

3.3. SEDATION/AIRWAY

Patients will undergo the procedure under deep sedation with an artificial airway (endotracheal tube, laryngeal mask airway or tracheostomy) in place. The use of a rigid bronchoscope will be left to the discretion of the physician performing the procedure. Deep sedation medications and route of administration are at the discretion of the sedating physician.

3.4. BRONCHOSCOPIC BIOPSY

Prior to induction of anesthesia, the 1.1mm flexible single-use cryoprobe will be connected to the ERBECRYO 2 unit via the plug (see IFU for full details). The cryoprobe should be tested as described in the instruction for use (IFU) by immersing the cryotip to a depth of at least 5 cm in sterile warm water at a temperature of approx. 20°C (68°F) and by activating the freeze function of the ERBECRYO 2 for approximately 5 seconds. A clearly visible, homogenous ball of ice must form at the cryotip when freezing capacity is sufficient. Gas bubbles must not escape under any circumstances. Once tested, induction of anesthesia may be performed.

Once appropriate sedation has been achieved and a secure airway has been placed, an airway inspection is to be performed. Following airway inspection and after the appropriate airway has been selected, the cryoprobe multiadapter will be secured to the working channel connector of the bronchoscope. The oversheath can then be inserted and secured to the multiadapter. The cryoprobe can then be inserted through the oversheath via the bronchoscope into the targeted airway using tactile control until in the targeted location is reached. It is optional to place a deflated prophylactic bronchial blocker prior to biopsy. The freeze function is then activated. The initial freeze time will be 4 seconds as measured on the device timer. At the discretion of the bronchoscopist, should inadequate tissue be collected due to incomplete freeze, the freeze time can be extended by 1 second on each consecutive attempt, up to a maximum of 8 seconds. The cryoprobe along with the biopsy specimen is removed with a jerk motion analogous to the same motion used for standard forceps. The sample is then extracted through the oversheath with the bronchoscope remaining in the airway, thereby maintaining freezing activation until the specimen is completely out of the bronchoscope. It is important, that the specimen is pulled quickly into the oversheath with the first movement as far as possible in order to squeeze soft tissue in the oversheath. The freeze function is then deactivated and the specimen should immediately

be placed in saline. The removal tool accompanying each cryoprobe can be used to carefully remove the specimen from the tip of the cryoprobe only after the specimen was defrosted. Specimens will then be transferred into a fixative (i.e. formalin) per institutional policy and sent to the local institutional pathology lab for processing and interpretation. Each biopsy sample will then be sent for central pathology interpretation. If tissue cultures are clinically indicated, an additional specimen may be placed in sterile saline

For non-lung transplant rejection related biopsies, a minimum of 3 biopsies must be taken using the 1.1mm sheath cryoprobe. For lung transplant rejection surveillance biopsies, a minimum of 5 cryobiopsies must be taken (more if needed), as per IHS LT guidelines, at least 5 pieces of well-expanded alveolated lung parenchyma are required for an assessment of acute rejection.⁹ As part of this study, only cryobiopsy with the 1.1mm single-use flexible cryoprobe with oversheath is permitted for transbronchial lung biopsy. This excludes the use of needle, forceps, and brush biopsy. In case of cryoprobe failure a new 1.1mm sheath cryoprobe should be used. A bronchoalveolar lavage or wash is allowed if clinically indicated but must be performed after the index procedure is performed.

Following the procedure, the patient will be returned to the post-anesthesia care unit and a post-procedural chest x-ray will be obtained and results will be documented.

3.5. COMBINED LOCALIZATION PROCEDURES

It is expected (in fact encouraged) that additional localization modalities in addition to standard optical bronchoscopy will be used in combination with the cryobiopsy as would be done with traditional biopsy techniques under standard of care. These include, but are not limited to, fluoroscopy, radial endobronchial ultrasound, and electromagnetic navigation. Robotic Bronchoscopy is excluded due to the fact that a standard flexible bronchoscope is not used. That said, as part of this trial, for tissue acquisition, the only biopsy tool permitted to be used is the cryoprobe. If convex EBUS with rapid onsite pathologic examination (ROSE) is being performed as part of the planned bronchoscopy, this should be performed prior to transbronchial cryobiopsy.

3.6. DATA COLLECTION

Collected data include: radiographic characteristics, procedural characteristics, diagnostic yield, and adverse events, as follows:

- *Radiographic Characteristics:*

If a target location is present (i.e. biopsy for lung nodule), the location of the target lesion (side, lobe and segment, i.e. right upper lobe anterior segment, etc.) will be determined and recorded. The radiographic information collected will include size of the lesion (longest axis), distance from a visible bronchus, and distance from the pleural surface perpendicular to the lesion on axial cuts. If the patient has undergone a PET scan, the metabolic activity (measured SUV) will be recorded.

If target lesions exists, to assess centrality, we will utilize proprietary software to map zones of the lung to determine if a lesion falls into the outer, middle, or central 1/3 of the lung parenchyma. "CT Pulmo 3D" workflow using Siemens Syngo via software automatically analyzes the lung parenchyma and define the contours of both lungs (Figure 1). This will be performed by the core radiology laboratory at Johns Hopkins. External sites to Johns Hopkins (Vanderbilt University) will submit the de-identified CT scan via a secure program (Ambra) that is in clinical use for secure image sharing.

[figure not shown]

Figure 2: CT Pulmo 3D software output defining central, middle and peripheral lung zones¹⁰

For diffuse lung disease, the CT characteristic pattern will be recorded (i.e. UIP, NSIP, cystic, reticular nodular). Additionally, localization and distribution of infiltrates will be collected. If no specific lung abnormalities are noted on CT (i.e. lung transplant surveillance), this will be recorded.

- **Procedural Characteristics:**

Collected procedural information will include the number of biopsy attempts, freeze time for each biopsy, procedural time (scope in to scope out) and use of prophylactic bronchial blocker. The type (general or moderate) of sedation administered as well as artificial airway selection (ETT, LMA, rigid bronchoscopy) will also be recorded. Room temperature and gas pressure, number of probes used.

- **Pathology Core Lab Assessment:**

An independent pathology core lab will review all study cases. The core lab will be graded on a previously validated histologic accessibility on a 7-point Likert Scale^{6,11} as follows:

- Grade 0: The specimen does not contain alveolar structures and can therefore not be assessed as transbronchial biopsy specimen
- Grade 1: Due to very poor specimen quality, it is not possible to assess the relevant morphologic and histologic features
- Grade 2: Due to poor specimen quality, assessment of relevant morphologic and histologic structures and features is severely compromised and not possible
- Grade 3: Despite high limitations in specimen quality, assessment of the relevant morphologic and histologic structures and features is severely compromised but possible
- Grade 4: Despite moderate limitations in specimen quality, assessment of the relevant morphologic and histologic structures and features is compromised but possible
- Grade 5: Despite low limitations in specimen quality, assessment of the relevant morphologic and histologic structures and features are compromised but possible

- Grade 6: The specimen allows for complete and unrestricted assessment of all relevant morphologic and histologic structures and features

Additionally, the pathologic core lab will determine, the total histologic area (mm²), alveolated area (mm²), open alveoli percent, percent crush artifact, and artifact free lung parenchyma percent. The underlying diagnosis will be confirmed or rebutted.

▪ *Diagnostic Yield:*

Diagnostic yield is defined as proportion of patients for which cryobiopsy led to a diagnosis. Diagnostic yield will be determined from the results of cryobiopsy specimen only. A biopsy that results in a specific diagnosis, either malignant or benign (granuloma, inflammation, fibrosis, infection) will be assumed to be a true positive. Atypia, minimal inflammation or lung parenchyma without pathologic findings on final pathology reads are considered non-diagnostic.

▪ *Room Temperature and Gas Pressure:*

The room temperature of the OR (by a thermometer fixed to the ERBECRYO 2 unit) and the gas pressure which is displayed on the cryo unit will be collected prior to the index procedure. This ensures standardized results throughout the study. The gas pressure and the room temperature must be at least 56bar and 68°F (20°C), respectively.

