2.1. OBJECTIVE AND PURPOSE

The objective of this study is to evaluate the safety profile of the new 1.1mm single-use flexible cryoprobe with oversheath for the sampling of lung tissue. The safety profile will be assessed across the

various indications for transbronchial lung biopsy (i.e. lung transplant rejection surveillance, lung nodule biopsy, diffuse parenchymal lung disease, pneumonitis). Safety will be assessed by collecting AE and SAE information up to 30 days.

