5.4.3. ANALYSIS OF THE SECONDARY ENDPOINTS(S)

1. Description of histologic performance. The mean histologic adequacy score, total histologic area (mm²), alveolated area (mm²), open alveoli percent, percent crush artifact, and artifact free lung parenchyma percent will be reported as mean (+/- SD) or Median (Range). This data will be used for statistical planning for future trials.
2. Procedural characteristics such as activation time, procedure time, number of biopsies taken and type of airway (proportion used LMA, ETT, rigid bronchoscope) used will be reported as mean (+/- SD) or Median (Range). Logistic regression will be used to determine if procedural characteristic significantly affect the presence of a significant adverse event (primary outcome). Additionally, linear regression will be used to determine if any of the procedural characteristics effect histologic performance characteristics.
3. Diagnostic yield of cryobiopsy will be calculated as the proportion of patients for which cryobiopsy led to a specific diagnosis. A biopsy will be considered diagnostic, if it results in a specific diagnosis, either malignant or benign (granuloma, inflammation, fibrosis, infection) will be assumed to be a true positive.

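### Grade 0 is given to any specimen without alveoli, nodule biopsies included, and 5.4.3 does not split by indication, so the accessibility grade and the alveolus-based measures are confounded by case mix

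*Combined protocol and SAP*

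**What the plan says.** - **Who is graded (3.6, Pathology Core Lab Assessment).** "An independent pathology core lab will review all study cases". The scale runs from 0 to 6.
- **Bottom of the scale.** "Grade 0: The specimen does not contain alveolar structures and can therefore not be assessed as transbronchial biopsy specimen". No separate rule is given for a specimen taken from a targeted lesion.
- **Top of the scale.** "Grade 6: The specimen allows for complete and unrestricted assessment of all relevant morphologic and histologic structures and features".
- **Other core-lab measures (3.6).** "total histologic area (mm²), alveolated area (mm²), open alveoli percent, percent crush artifact, and artifact free lung parenchyma percent".
- **Diagnostic yield (3.6).** A specific malignant or benign histologic diagnosis from the cryobiopsy counts as a true positive.
- **Population (2.1).** The indications are "lung transplant rejection surveillance, lung nodule biopsy, diffuse parenchymal lung disease, pneumonitis". No share or quota is set for any of them.
- **Targeting (3.5).** "It is expected (in fact encouraged) that additional localization modalities in addition to standard optical bronchoscopy will be used".
- **Summaries (5.4.3 item 1).** Each histology measure is reported as a mean with SD or a median with range. No subgroup is named, and "This data will be used for statistical planning for future trials". This item calls the score adequacy; I take it to be the accessibility grade, since no other score is defined.
- **Regression (5.4.3 item 2).** Histologic performance is regressed on procedural characteristics, and the characteristics listed in that item include the number of biopsies. No indication term is named. Section 3.4 sets a minimum of 5 cryobiopsies for transplant surveillance and 3 otherwise.

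**The concern.** A biopsy that lands wholly inside a solid nodule may contain lesion and no alveoli. Under the grading rule it then scores the same as a specimen that missed the lung parenchyma, while the yield definition in the same section can count it as a success. Two secondary endpoints move in opposite directions on one sample. Zero alveolated area is a true measurement for such a specimen, but averaged with transplant and diffuse-disease biopsies it reads as poor tissue quality.

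The pooled grade, alveolated area, open alveoli percent and probably artifact-free parenchyma percent therefore depend on how many nodule patients happen to be enrolled and how often the probe sits fully in the lesion. These summaries are meant to inform later trials. A planner with a different case mix could not recover the figure that applies to it.

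The regression is exposed in the same way. Minimum biopsy count and nodule status both vary with indication, so an effect of biopsy number could appear that is only case mix.

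**Working it through.** The plan gives no target, mean, SD or power for any histology measure, so there is no figure to reproduce. The check is to apply the grading rule to a mixture of specimens.

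**Inputs, all assumed except the biopsy counts.**
- s: share of specimens from nodules.
- q: share of nodule specimens that are lesion only, hence Grade 0.
- g: mean grade of all other specimens.
- Minimum biopsy counts of 3 and 5, from 3.4.

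**Pooled mean grade** = g × (1 − s × q). For any s and g above zero it falls as q rises. With g = 5:

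| s | q = 0 | q = 0.5 | q = 1 |
|---|---|---|---|
| 0.2 | 5.0 | 4.5 | 4.0 |
| 0.4 | 5.0 | 4.0 | 3.0 |
| 0.6 | 5.0 | 3.5 | 2.0 |

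The proportional fall is s × q whatever g is: at s = 0.4, q = 0.5 the mean is 3.2 for g = 4 and 4.8 for g = 6, both 20% lower. If lesion-only specimens enter as zero, and nodule and other specimens are otherwise alike, mean alveolated area and open alveoli percent shrink by the same factor. Total histologic area and percent crush artifact have no such link.

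**Unit of analysis.** The plan does not say whether the grade is summarised per specimen or per patient. Take 40% nodule, 30% transplant and 30% other patients at the minimum counts:
- Nodule share of specimens = (3 × 0.4) / (3 × 0.4 + 3 × 0.3 + 5 × 0.3) = 1.2 / 3.6 = 0.333.
- Per-specimen mean at q = 0.5 is 5 × (1 − 0.333 × 0.5) = 4.17, against 4.0 if each patient contributes the mean of their own specimens.

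The effect is smaller but has the same direction.

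**Regression.** Keep those shares, q = 0.5, g = 5, exactly the minimum number of biopsies each, and no real effect of biopsy number:
- Mean grade at 3 biopsies = (0.4 × 2.5 + 0.3 × 5) / 0.7 = 3.57.
- Mean grade at 5 biopsies = 5.
- Apparent slope = (5 − 3.57) / 2 = 0.71 grade per extra biopsy, produced by case mix alone. With a nodule/non-nodule term it is zero, because all non-nodule patients average 5.

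**The case against.** **The size rests on invented inputs.** This stands. The documents give no nodule share, lesion-only frequency or grade distribution. A nodule specimen with any adjacent alveolar tissue escapes Grade 0. If lesion-only specimens are rare, the effect is close to nil. Scoring each patient by the best specimen would also shrink it: with three independent specimens, each lesion only with probability 0.5, and 30% nodule patients, 0.5³ × 30% = 3.75% of patients would be at Grade 0, not 15%.

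**The median is permitted.** True, and it is robust. With 15% of scores at 0 and the rest normal with mean 5 and SD 1, the median is about 4.8. But 5.4.1 reports continuous data as means with SDs, 5.4.3 leaves the choice open, and item 1 names a mean score.

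**Reporting by indication may be intended.** Section 5.2 speaks of descriptive data across disease states, and 3.6 records target-lesion details. That makes a split possible; no analysis rule requires it.

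**The core lab might grade a nodule on its lesional features.** The Grade 6 wording could be read that way, but the Grade 0 wording has no exception. Leaving graders to choose between opposite ends of the scale is no remedy.

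**A reader might infer that a future trial would be about four times too large.** The arithmetic behind that is a variance of 0.85 × 1 + 0.85 × 0.15 × 25 = 4.04 against 1. The conclusion does not follow. A trial with the same scale and case mix would face that larger SD, so sizing on it would be right. The documents also do not say that a later trial will be powered on this grade.

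**A reader might infer that the scale was never validated for this use.** By title, its two cited sources are a porcine lung study and a study of EUS-guided pancreatic biopsy. The protocol calls the scale validated, and the contents of those sources cannot be checked here.

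**Conclusion.** The point holds as a confounding problem in descriptive secondary endpoints. The text fixes the direction: a lesion-only nodule specimen gets the lowest grade and zero alveolated area whatever its diagnostic value, and nothing in 5.4.3 separates it from the rest. The accessibility grade, alveolated area, open alveoli percent and probably artifact-free parenchyma percent are affected, together with the histology regression.

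The size cannot be stated. The fall of 0.5 to 1.5 grades for s between 0.2 and 0.6 depends on q = 0.5 and g = 5, neither of which the documents supply.

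Two stronger readings are not supported. The scale is not reversed for nodules as a whole: Grades 1 to 6 rank assessability in the usual direction, and only the Grade 0 entry condition misfires. Nor does the pooled score measure case mix in place of probe performance; it mixes the two. Total histologic area and crush artifact need not change. The primary safety endpoint is unaffected, and diagnostic yield still credits the diagnostic specimen.

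**What to change.** - **3.6.** Keep the cited 0–6 scale and its Grade 0 definition. Add a flag on the core-lab form for Grade 0 specimens from nodule biopsies that contain lesional tissue.
- **5.4.3 item 1.** Report the grade and the alveolus-based measures separately for nodule and non-nodule biopsies. Give lesion-only specimens as their own count, not averaged in as failures. State whether the unit is the specimen or the patient.
- **5.4.3 item 2.** Include indication in the histology regression and handle lesion-only specimens in the same way there.

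Rewriting Grades 1 to 6 to cover lesional tissue is not needed. It would depart from the cited scale and would let a nodule biopsy that missed into normal lung score 6.

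The split uses target-lesion information already collected, and the flag is one item on a review already planned. No extra patients, samples or reads are needed, provided the flag is in place before core-lab grading starts. The cost is smaller strata. With 40% nodule patients among 50, the groups are 20 and 30. For an assumed SD of 1 and one score per patient, the 95% half-width for a mean is 1.96/√20 = 0.44 and 1.96/√30 = 0.36, against 1.96/√50 = 0.28 pooled. The biopsy-number coefficient will also be less precise once indication is in the model.

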1. BACKGROUND

The current standard method for obtaining bronchoscopic lung biopsy specimens is transbronchial forceps biopsy (FBx). However, the utility and diagnostic capability of FBx is limited by poor specimen quality due to small biopsy size, crush artifact and cellular artifact.¹ In part due to these restraints, the diagnostic yield of FBx has remained limited to 34-58% in diffuse lung disease¹⁻³ and 54-58% for pulmonary nodules^{4,5}. With the promise of obtaining higher quality tissue samples, cryoprobe biopsy (CBx) offers a similarly minimal invasive alternative to standard FBx.

Cryoprobe have been used in the bronchoscopic management of malignant endobronchial disease and for transbronchial biopsy. The CBx operates using the Joule-Thomson effect, in which compressed gas undergoes adiabatic expansion and rapidly cools the probe's tip. This allows for adequate anchoring of the probe to lung parenchyma and biopsy specimen retrieval. There have been numerous recent studies evaluating the performance of CBx. Higher diagnostic yields and larger biopsy sizes with better quality have been observed using CBx over FBx^{2,3,6-8}. However, these benefits might come at a cost of higher complication rates, specifically, higher bleeding risks.

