2.3. SECONDARY ENDPOINTS

Secondary Outcomes will include (for definitions, see Data Collection):

- 1) Mild or Moderate Adverse Events: Rate of bleeding grade ≤ 2 , pneumothorax not requiring chest tube placement (Grade 1)
- 2) Histologic Accessibility Grade
- 3) Total Histologic area (mm^2)
- 4) Alveolated Area (mm^2)
- 5) Open alveoli percent
- 6) Percent crush artifact
- 7) Artifact free lung parenchyma percent
- 8) Activation time
- 9) Diagnostic Yield: defined as proportion of patients for which the cryobiopsy sample led to a specific diagnosis on histologic examination
- 10) Procedure time

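### The diagnostic-yield rule takes fibrosis, and inflammation beyond an undefined minimal level, as true positives in every indication, so a nodule cancer missed with such a reading can be counted as diagnostic

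*Combined protocol and SAP*

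**What the plan says.** Section 2.3 makes diagnostic yield the ninth of ten secondary outcomes: "proportion of patients for which the cryobiopsy sample led to a specific diagnosis on histologic examination". Section 3.6 says what counts: "A biopsy that results in a specific diagnosis, either malignant or benign (granuloma, inflammation, fibrosis, infection) will be assumed to be a true positive". It then limits this: "Atypia, minimal inflammation or lung parenchyma without pathologic findings on final pathology reads are considered non-diagnostic". It also fixes the source of the result: "Diagnostic yield will be determined from the results of cryobiopsy specimen only". Of the pathology core lab it says: "The underlying diagnosis will be confirmed or rebutted".

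Section 5.4.3 repeats the positive half of the rule, "A biopsy will be considered diagnostic, if it results in a specific diagnosis, either malignant or benign (granuloma, inflammation, fibrosis, infection", and the assumption that such results are true positives, but not the list of non-diagnostic readings.

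Section 2.1 names the indications as transplant surveillance, nodules, diffuse parenchymal disease and pneumonitis. No definition of yield varies between them. The synopsis sets participation at 30 days, and 2.1 and 3.7.6 describe follow-up for adverse events, by chart review or, failing that, by telephone. Section 5.4.1 promises sensitivity, specificity, both predictive values and accuracy, and names no reference standard.

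**The concern.** Inflammation and fibrosis can answer the clinical question in diffuse disease or pneumonitis. In a patient biopsied for a nodule, neither names an entity that explains the lesion, and either may be found in tissue beside a lesion that was missed. The rule treats both situations alike and takes the reading as correct.

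What is at stake is the use of the data. The synopsis says the trial will generate preliminary efficacy data, 5.2 gives the descriptive results a role in planning later trials, and 5.4.1 says secondary outcomes will be used to power them. A nodule yield that contains unverified benign readings would carry its bias into those calculations. The accuracy measures in 5.4.1 would inherit the same assumption.

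**Working it through.** The plan states no target, precision or expected value for yield, so there is no figure to reproduce. The check has four steps.

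**1. How each reading is scored**

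| Reading of the cryobiopsy | Section 3.6 | Section 5.4.3 |
|---|---|---|
| Malignancy | diagnostic | diagnostic |
| Granuloma, infection | diagnostic | diagnostic |
| Fibrosis, any extent | diagnostic | diagnostic |
| Inflammation beyond minimal | diagnostic | diagnostic |
| Minimal inflammation | non-diagnostic; boundary not defined | not mentioned |
| Atypia, normal parenchyma | non-diagnostic | not mentioned |

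The third and fourth rows apply to nodules as to every other indication.

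**2. Whether anything could later change the score**

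Yield is confined to the cryobiopsy specimen. Core-lab review is described without any clinical or imaging follow-up. Sections 3.4 and 3.5 exclude other transbronchial biopsy tools, so there is no parallel sample of the lesion. Follow-up is for adverse events to 30 days. No repeat imaging, repeat biopsy, surgical result or final clinical diagnosis is planned as a check on a benign reading.

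**3. Accuracy measures**

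PPV = TP / (TP + FP). If every diagnostic result is taken as true, FP = 0 and PPV = 100% whatever the device does. For the same reason specificity, TN / (TN + FP), can only be 100% or undefined. Sensitivity and NPV need the true status of patients with a non-diagnostic biopsy, which the plan does not obtain.

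**4. Size**

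Only N = 50 is from the documents (5.7). The other inputs are assumptions:
- m, number of nodule patients: 10 to 30
- f, share of nodule biopsies scored diagnostic as inflammation or fibrosis: 10% to 30%
- q, share of those readings that prove to be cancer: 10% to 50%

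Overstatement of nodule yield = f × q. Overstatement of overall yield = (m/50) × f × q.

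| Case | m | f | q | Nodule yield | Overall yield | Patients (m × f × q) |
|---|---|---|---|---|---|---|
| Low | 10 | 0.10 | 0.10 | 1 point | 0.2 points | 0.1 |
| Middle | 20 | 0.20 | 0.30 | 6 points | 2.4 points | 1.2 |
| High | 30 | 0.30 | 0.50 | 15 points | 9 points | 4.5 |

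For PPV, assume also that 40% of nodule biopsies are read as malignant and that there are no other benign diagnoses. Verified PPV = (0.40 + f(1 − q)) / (0.40 + f):
- low: 0.49/0.50 = 98%
- middle: 0.54/0.60 = 90%
- high: 0.55/0.70 = 79%

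The rule returns 100% in all three.

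The gap between a liberal and a strict definition is a different quantity, because it moves every non-specific reading, benign or not. With an assumed 20 nodule patients, 2, 5 or 8 such readings shift nodule yield by 2/20, 5/20 or 8/20 = 10, 25 or 40 points, and overall yield by 2/50, 5/50 or 8/50 = 4, 10 or 16 points.

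For scale, 29/50 = 58% has an exact 95% interval of 43% to 72%. The lower limit is 15 points and the upper 14 points from the estimate, both more than the 9-point overall bias in the high case.

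**The case against.** The strongest reply is that the plan does limit the rule. A reader might infer that any inflammation counts and that missed cancers are scored as successes as a matter of course. The documents do not support that. A miss read as atypia, minimal inflammation or normal parenchyma is a failure under 3.6, and the listed readings stand under the requirement of a specific diagnosis. What remains is that the minimal boundary is undefined, fibrosis has no limit, and the analysis section drops the exclusions.

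A reader might also take the 10 to 40 point shift as the error. It is the effect of changing the definition on an assumed case mix, and it counts truly benign inflammatory or fibrotic lesions as mistakes.

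Nor can it be said that a gain over the forceps yield cited in section 1, "54-58% for pulmonary nodules", would be an artefact. The documents do not say how that figure was defined, and no comparison with it is planned. The comparison is only uninterpretable until the definitions are matched.

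It is fair to add that yield is one of ten secondary outcomes in a safety study that 5.1 says is not powered for a statistical conclusion, that 5.2 plans yield for different diseases, and that strict versus liberal yield is partly a matter of choice. Yield can be defined on the specimen alone, but then the plan should not also call the result true. The sampling-error argument carries limited weight: this bias does not shrink with more patients, and in the nodule group it can be material.

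**Conclusion.** The concern holds in a limited form. Fibrosis, and inflammation above an undefined minimum, are taken as correct in every indication, and nothing planned would reclassify a nodule cancer missed with such a reading. Such a case can be counted as diagnostic; the documents do not show how often it would be. Under the assumed ranges, nodule yield is overstated by about 1 to 15 points and overall yield by 0.2 to 9; the middle case is 6 and 2.4 points, or roughly one patient in 50. The definitional gap may be larger.

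The primary safety endpoint does not use yield, so its conclusion is unaffected. The harm is confined to preliminary yield data intended for later planning, and to accuracy measures that have no reference standard.

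**What to change.** In 3.6 and 5.4.3:
- For patients with a recorded target lesion, report two figures. The strict one counts malignancy or a specific benign entity such as granuloma or infection, and treats inflammation or fibrosis alone as non-diagnostic. The liberal one is the present rule.
- Report yield by indication. Include transplant surveillance, where normal parenchyma may be the informative answer yet is scored as non-diagnostic.
- Carry the list of non-diagnostic readings into 5.4.3.
- Delete the true-positive assumption from both sections.

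In 5.4.1, drop the accuracy measures for yield unless a reference standard is stated.

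Target lesions and pathology readings are already collected under 3.6, so no new procedure is needed unless the sponsor chooses to verify benign readings by longer follow-up. The cost is slightly more tabulation and a lower headline yield in nodules.
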